--	-----------------------------------------------------------------------------------------------------------------------------------------------------------------------------------------------------------------------------------------------------------------------------------------------------------------------------------------------------------------------------------------------------------------------------------------------------------------------------------------------------------------------------------------------------------------------------------------------------------------------------------------------------------------------------------------------------------------------------------------------------------------------------------------------------------------------------------------------------------------------------------------------------------------------------------------------------------------------------------------------------------------------------------------------------------------------------------------------------------------------------------------------------------------------------------------------------------------------------------------------------------------------------------------------------------------------------------------------------------------------------------------------------------------------------------------------------------------------------------------------------------------------------------------------------------------------------------------------------------------------------------------------------------------------------------------------------------------------------------------------------------------------------------------------------------------------------------------------------------

		
repeat from the wording in the IB.
 
Changed the name of the insulin ± metformin sub-study to insulin with or without metformin sub-study to increase clarity about entry requirements.
 
Removed the requirement that for a subject to meet the criterion of either progression or regression of albuminuria, the albuminuria threshold had to be met at two consecutive visits.
 
Clarified in Section 9.7 that only the results of the meta-analysis (Stage 1) will be submitted to regulatory authorities while the main study is ongoing.
 
Added a superiority analysis for the composite endpoint of renal death, renal dialysis/transplant or ≥2x increase in baseline serum creatinine.

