1.2.2. Safety of Ertugliflozin and SGLT2 Inhibitors

The SGLT2 inhibitors dapagliflozin, canagliflozin and empagliflozin are approved in the US and in the European Union. Based on available clinical trial data with dapagliflozin, canagliflozin and empagliflozin, several potential risks from SGLT2 inhibition have been identified. In clinical trials, the rate of genital fungal infections in males and females has consistently been higher in subjects receiving SGLT2 inhibitors as compared to placebo or other diabetes medications. Therefore, the increased risk of genital fungal infections can be considered a class effect of SGLT2 inhibitors. Glucosuria can potentially result in increased risk of urinary tract infection (UTI) and this adverse drug reaction was commonly reported in clinical trials with marketed SGLT2 inhibitors. Most infections were mild to moderate in severity and infections were reported more frequently in females than in males. There have also been postmarketing reports of serious UTIs including urosepsis and pyelonephritis requiring hospitalization in patients receiving marketed SGLT2 inhibitors.

SGLT2 inhibition results in an osmotic diuresis, which may lead to reductions in intravascular volume and a small decrease in blood pressure. In clinical trials with marketed SGLT2 inhibitors, treatment was associated with an increase in the incidence of adverse events related to volume depletion (eg, dehydration, hypovolemia, hypotension, orthostatic hypotension, syncope, postural dizziness). These events occurred at higher frequency and were more pronounced in some populations. As SGLT2 inhibition can lead to volume depletion, there is a concern for potential adverse renal effects. In clinical trials with marketed SGLT2 inhibitors, early declines in the estimated glomerular filtration rate (eGFR) were seen, although there was a return toward baseline levels over time during treatment and upon discontinuation of therapy. This early eGFR decline is believed to be related to dehydration and not due to progressing renal insufficiency. However, the pattern of eGFR decline appeared to be different in subjects with varying degrees of baseline renal function, with greater persistence of eGFR decline in subjects with moderate renal impairment. In addition, in subjects with moderate renal impairment there was a slightly higher incidence of renally-related adverse events reported in subjects receiving SGLT2 inhibitors than in controls.

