2.6.2. Secondary Endpoints

- Time to first occurrence of:
 - Cardiovascular death or hospitalization for heart failure;
 - Cardiovascular death;
 - MACE plus;
 - Fatal or non-fatal myocardial infarction;
 - Fatal or non-fatal stroke;
 - Hospitalization for heart failure;
 - Individual components of MACE (cardiovascular death, non-fatal myocardial infarction, non-fatal stroke).

- All-cause mortality.
- All MACE events (ie, not censored at the time of the first event).
- All cardiovascular death or hospitalizations for heart failure (ie, not censored at the time of the first event).
- Time to first occurrence of the composite of renal death, renal dialysis/transplant, or $\geq 2x$ increase in baseline serum creatinine.

When added to usual background therapy in subjects with T2DM and established vascular disease:

- Change from Baseline in HbA1c at Week 18, Week 52 and annually thereafter.
- Proportion of subjects with HbA1c $< 7\%$ (53 mmol/mol) and $< 6.5\%$ (48 mmol/mol) at 12, 24 and 36 months and annually thereafter.
- Time to the first occurrence of a subject receiving glycemic rescue therapy during the first 18 weeks of the study.
- Time to initiation of insulin for subjects not on insulin at randomization.
- Change in insulin dose from Baseline at Week 18, Week 52 and annually thereafter.
- Change from Baseline in systolic and diastolic blood pressure at Week 18, Week 52 and annually thereafter.
- Change from Baseline in body weight at Week 18, Week 52 and annually thereafter.
- Change from Baseline in eGFR and serum creatinine at Week 18, Week 52 and annually thereafter.
- Change from Baseline in albuminuria as measured by the urinary albumin to creatinine ratio at Week 18, Week 52 and annually thereafter stratified by albuminuria category at baseline (normoalbuminuria, microalbuminuria and macroalbuminuria).
- Progression of nephropathy as measured by the progression of normoalbuminuria to microalbuminuria and/or macroalbuminuria as well as measurement of regression of albuminuria (eg, macroalbuminuria \rightarrow microalbuminuria).

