6.7.4. Reasons for Discontinuation from Investigational Product or from the Trial

The investigator or sub-investigator is able to interrupt or discontinue investigational product if he/she feels that interruption or discontinuation is necessary for safety or behavioral reasons. The investigational product can also be restarted based on the judgment of the investigator. Notably, occurrence of a non-fatal cardiovascular event or a SAE should not automatically result in interruption or discontinuation of investigational product and the subject should continue to receive investigational product unless interruption or discontinuation is deemed to be clinically necessary.

Reasons for protocol-specified discontinuation from the investigational product or from the trial are listed, but not limited to, below. All subjects will be followed until resolution (ie, return to baseline values or diagnosis determined or new stable state established, based upon investigator and sponsor or its designated representative assessment) for any laboratory safety test abnormality resulting in discontinuation from investigational product.

Withdrawal from the Trial

1. Subject requests withdrawal from the trial.
2. Death.

090177e187d04317\Approved\Approved On: 14-Mar-2016 14:12

Discontinuation of Investigational Product

3. Elevation in ALT and/or AST that meet the definition of a potential Case of Drug-Induced Liver Injury per [Section 8.7](#).
4. Parameters of Renal Function: Investigational product is to be discontinued if the eGFR falls to $<15 \text{ mL/min/1.73m}^2$ and where the value is confirmed by a second measurement. Additionally, any subject who requires renal replacement therapy will also have investigational product discontinued.

A confirmed value is defined as a repeat measurement performed within 7 days of notification from the central laboratory of the initial results.

5. Requirement for one of the prohibited medications listed in [Section 4.2](#).
6. Pregnancy.

Note: A positive urine pregnancy test requires immediate interruption of investigational product until serum human chorionic gonadotropin beta-subunit test (β -hCG) can be performed and found to be negative. Subject must be permanently discontinued and pregnancy should be reported and followed per [Section 8.3](#) if pregnancy is confirmed by a positive serum pregnancy test.

7. The investigator or subject becomes aware of the subject's treatment assignment.

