7.1. Clinical Event Adjudication

7.1.1. Cardiovascular Events, Venous Thromboembolic Events, and All Deaths

Cardiovascular disease is a major cause of mortality for subjects with T2DM. In order to evaluate the cardiovascular safety of ertugliflozin and to meet regulatory requirements for the assessment of cardiovascular safety of any new diabetic therapy, serious cardiovascular events and all deaths will be adjudicated in this trial (including events from subjects who continue to be followed after discontinuation of investigational product), and across the Phase 2 and 3 ertugliflozin program. The EAC will be comprised of an external panel of independent physicians experienced in assessing cardiovascular endpoints. The panel will be blinded to treatment assignments. The members of the EAC will not be an investigator in any trial for ertugliflozin. The events to be adjudicated by the committee include:

1. All deaths;
2. Non-fatal myocardial infarction; hospitalization for chest pain or to rule out myocardial infarction, or other hospitalization due to suspected myocardial ischemia where myocardial infarction needs to be ruled out;
3. Non-fatal stroke (and all events that may be a stroke including all transient ischemic attack (TIA) events, reversible ischemic neurologic deficit (RIND) or other acute ischemic cerebrovascular event where stroke needs to be ruled out);
4. Hospitalization for unstable angina;
5. Hospitalization for heart failure;
6. Venous thromboembolism/pulmonary embolus.

The criteria to define clinical cardiovascular events will be detailed in the Endpoint Adjudication Committee charter. All potential clinical cardiovascular events will be collected from the first day of double-blind treatment through the end of study (including 14 day post-dose reporting period) for all randomized subjects who have received at least one dose of investigational product. The collection period will continue through study completion/end-of-study whether or not the subject continues to receive investigational product unless the subject is unwilling to be contacted by the personnel at the investigational site.

Clinical cardiovascular events occurring between the Screening visit (the time of informed consent) and double-blind treatment randomization will not be adjudicated as that subject will be excluded from the trial as per [Section 4.2](#).

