7.1.5. Acute Renal Failure

Ertugliflozin increases urinary glucose excretion leading to an osmotic diuresis, and has the potential to reduce estimated GFR. As part of the overall assessment of renal safety, events reported in this trial and throughout the phase 3 program that meet pre-specified criteria for potentially important renal failure events will be adjudicated by an external independent panel of physicians experienced in adjudication of renal events. The panel will be blinded to treatment assignment and will assess causality. A Renal Failure Adjudication Charter will

090177e187d04317\Approved\Approved On: 14-Mar-2016 14:12

describe the precise mandates and procedures to be used for assessing renal failure and assigning causality.

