9.2. Primary Cardiovascular Endpoints Analysis

The two doses of ertugliflozin will be pooled for the analysis of cardiovascular endpoints. The analyses described below will be performed at the interim analysis and at the end of the trial.

The Stage 1 meta-analysis population will include all randomized subjects who have taken at least one dose of investigational product across the Phase 2 and 3 development program. The Stage 2 non-inferiority analysis population will include all randomized subjects who have taken at least one dose of investigational product in this study. For both stages, subjects will be analyzed in the group to which they were assigned by IVRS, regardless of the actual treatment received and only events confirmed by the Endpoint Adjudication Committee will be included in the analysis. For Stage 1, all confirmed MACE plus events will be included in the primary analysis. For Stage 2, confirmed MACE events occurring between randomization and 365 days after the last dose of study treatment will be included in the primary non-inferiority analysis.

The MACE plus and MACE endpoints will be analyzed using a stratified Cox proportional hazards model including treatment group as a covariate. For the Stage 1 meta-analyses, the Cox model will include “Study” as a stratification factor with the following three levels: cardiovascular study, placebo-controlled non-cardiovascular studies, and active-controlled non-cardiovascular studies. For the Stage 2 analyses, the Cox model will include “Cohort” as the stratification factor with the following levels: Cohort 1 (subjects randomized between December 2013 and July 2015) and Cohort 2 (subjects randomized in 2016 and beyond). A test of non-inferiority at the one-sided 0.025 significance level will be performed based on the Cox model. The upper bound of the alpha-adjusted two-sided confidence interval (CI) for the hazard ratio (HR) (ertugliflozin to a non ertugliflozin comparator group or placebo) will be calculated using an O’Brien-Fleming alpha spending function and compared with the appropriate non-inferiority margin (1.8 or 1.3).

Kaplan-Meier curves for the distribution of time to MACE and MACE plus will also be provided for each of the three treatment groups.

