9.3. Secondary Endpoints Analysis

Secondary time-to-event endpoints (eg, fatal and non-fatal myocardial infarction, fatal and non-fatal stroke, hospitalization for heart failure, cardiovascular death, the composite of cardiovascular death or hospitalization for heart failure, the renal composite, and all-cause mortality) will be analyzed using Cox proportional hazards models with the same model terms as those included for the primary endpoint. A point estimate and two-sided nominal 95% confidence interval for the hazard ratio will be calculated based on the Cox model for

090177e187d04317\Approved\Approved On: 14-Mar-2016 14:12

each endpoint. Kaplan-Meier methodology will be used to estimate event rates over time for each treatment group.

If non-inferiority at the 1.3 margin is established for the primary MACE endpoint based solely on this study, then tests of superiority on the secondary endpoints of cardiovascular death or hospitalization for heart failure (composite), cardiovascular death (individual component), and the renal composite will also be performed. The population for superiority testing will include all randomized subjects and include all confirmed events, including those occurring more than 365 days following discontinuation of investigational product. Superiority tests will be implemented by comparing the upper bound of the appropriate alpha-adjusted two-sided CI to 1.0.

In order to control the Type I error rate across multiple hypotheses in Stage 2, a four-step hierarchical testing sequence for the pooled ertugliflozin group versus the placebo group will be utilized as follows:

1. Non-inferiority for MACE;
2. Superiority for cardiovascular death or hospitalization for heart failure (composite);
3. Superiority for cardiovascular death (individual component);
4. Superiority for composite of renal death, renal dialysis/transplant, or $\geq 2x$ increase in baseline serum creatinine.

If the result of the test at any step of the sequence is not statistically significant, then testing will stop so that tests further down in the sequence will not be conducted, and the corresponding null hypotheses will not be rejected. The alpha spending to be utilized for the interim and final analyses of the primary and secondary endpoints is described in [Section 9.7](#).

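### Does the renal composite (test 4) need a confirmation rule for creatinine doubling, dialysis and transplant?

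*Protocol*

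**What the plan says.** Protocol 2.6.2 lists the endpoint as "Time to first occurrence of the composite of renal death, renal dialysis/transplant, or" a creatinine at least twice baseline. Section 9.3 makes it the fourth and last step of the Stage 2 hierarchy. For all the superiority tests it says "The population for superiority testing will include all randomized subjects and include all confirmed events", including events more than 365 days after stopping drug.

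The word *confirmed* is explained elsewhere, for other endpoints:

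- Section 9.2, on the MACE and MACE plus analyses: "only events confirmed by the Endpoint Adjudication Committee will be included in the analysis".
- Section 2.6 limits the adjudicated-and-confirmed requirement to cardiovascular event data.
- Section 7.1.1 opens its list with "The events to be adjudicated by the committee include". The list covers all deaths, cardiovascular events and venous thromboembolism. It has no creatinine, dialysis or transplant item.
- Section 7.1.5 sends to a separate blinded panel those events that "meet pre-specified criteria for potentially important renal failure events will be adjudicated by an external independent panel of physicians". The purpose given is renal safety, and details are left to a charter.
- Section 6.7.4 has a repeat-value rule, "A confirmed value is defined as a repeat measurement performed within 7 days of notification from the central laboratory of the initial results", which serves the eGFR criterion for stopping drug.

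The power statement in 9.1 assumes at least 144 and 190 renal composite events at the interim and final analyses, a hazard ratio of 0.65 and about 79% power.

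**The concern.** Test 4 carries formal alpha, yet the supplied text does not say what turns a laboratory value into an event. Three readings can be put forward. If *confirmed* means confirmed by the cardiovascular committee, no doubling could ever count. If it means any central-laboratory value, one transient value counts. If it means a repeat value, no interval is given.

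The protocol also gives a reason to think of reversible changes. Section 1.2.2 reports early eGFR falls with this drug class that tend to return toward baseline, and adds "This early eGFR decline is believed to be related to dehydration and not due to progressing renal insufficiency". If enough such episodes reached a doubling, they would dilute the treatment effect on the composite and cost power. A rule left open until after unblinding would also allow a choice made with results in view.

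**Working it through.** **The passages together.** The first reading fails on the protocol's own terms. Section 9.2 concerns the primary cardiovascular endpoints and section 2.6 confines adjudication to cardiovascular data, so neither governs a laboratory component. The third reading borrows the 7-day repeat from a rule about stopping drug. What remains is the endpoint as worded in 2.6.2 and 9.3: a creatinine at least twice baseline, with no persistence condition. An analyst would count the first such value. The sentence in 9.3 that contains *confirmed* sets the population and follow-up window; it does not define endpoints.

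**The plan's power.** Inputs: 144 and 190 events and HR 0.65 (section 9.1); two-sided alpha of 2% then 4.4% (alpha table in 9.7); 1:1:1 randomization with doses pooled, so 2:1 against placebo.

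- Information per event: (2/3)(1/3) = 2/9.
- Expected Z at a look: −ln(HR) × √(events × 2/9), with −ln(0.65) = 0.431.
- Interim: 0.431 × √(144 × 2/9) = 2.44, against a bound of 2.326 (1% one-sided).
- Final: 0.431 × √(190 × 2/9) = 2.80, against a bound of 2.014 (2.2% one-sided).
- Correlation of the looks: √(144/190) = 0.871.
- Probability of crossing at either look: **79.2%**, against the stated 79%.

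**Effect of transient doublings (illustration).** Assume a share *s* of placebo events is transient, with HR 1.0, on top of 190 lasting events at HR 0.65. Adding them is reasonable because the MACE count triggers the analyses. Lasting placebo events are 190/(1 + 2 × 0.65) = 82.6. Transient events across the three arms are 3 × 82.6 × *s*/(1 − *s*). The composite HR is 0.65(1 − *s*) + *s*. The interim stays at 144/190 of the total.

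| Share *s* | Total events | Composite HR | Power, any doubling counts | Lasting events a persistence rule may lose before it does worse |
|---|---|---|---|---|
| 5% | 203.0 | 0.668 | 76.7% | 5.9% (178.8 left) |
| 10% | 217.5 | 0.685 | 74.1% | 11.7% (167.8 left) |
| 20% | 252.0 | 0.720 | 68.2% | 22.9% (146.5 left) |

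The last column is the loss at which power with lasting events alone, at HR 0.65, equals the power in the column before it. For comparison, losing 10% of lasting events leaves 171 events and 74.9% power.

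The convention matters. If transient events are instead 5%, 10% or 20% of all counted events and the total is held at 190, the HR is 0.664, 0.677 or 0.706 and power is 75%, 71% or 61%. If the planned HR of 0.65 already describes the composite as written, transient values included, 79% stands unchanged.

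**What a persistence rule would do.** Accepting the next available creatinine as confirmation sets no fixed interval. Section 7.11 calls for a retest one week after the early termination or end-of-study visit when drug is stopped for renal reasons, so, if the central laboratory runs that sample, it could confirm an acute episode. Routine visits after year 1 are four months apart. Subjects off drug may be seen annually or followed by phone (Schedule of Activities, footnote p; section 6.6). Stringency would then depend on drug status and type of follow-up.

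**The case for a change.** The best case for acting is that an endpoint with formal alpha should state its event rule, that doing so is cheap, and that the protocol writes a confirmation rule when it wants one, as in 6.7.4. No supplied passage links the renal panel to the composite. The SAP supplement's extract of the primary SAP gives only the analysis sets, method and windows for this endpoint. Chemistry is drawn at every clinic visit, so a persistence rule would need no extra scheduled samples.

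The observation that the text is silent stands. The step from silence to defect does not. Section 9 of the protocol defers detail to a statistical analysis plan, and the supplied SAP describes itself as a heart-failure supplement to the primary one. The primary SAP, the Renal Failure Adjudication Charter and the Endpoint Adjudication Manual may each hold the rule. Single-value counting may also be intended: the summary of Amendment 1, which added this test, reports dropping the requirement that "the albuminuria threshold had to be met at two consecutive visits". That concerns a different endpoint and settles nothing here, but it is a reason not to presume that persistence was meant.

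**Conclusion.** No change to the plan is needed. The supplied text leaves out a detail that an analyst can fill by taking the endpoint at its word, and other trial documents may already supply it. Counting the first doubling gives a usable rule. Transient doublings that are unrelated to treatment pull the hazard ratio toward 1, which works against a superiority claim. The cost is at most some power on test 4, which is reached only after three earlier successes; the action table in 9.7 also lets the study stop at the interim whatever the renal result. Tests 1 to 3 and the Type I error of the hierarchy are unaffected.

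The size of any power loss cannot be known from the documents. The 77%, 74% and 68% rest on assumed shares, a transient hazard ratio of 1.0 and the premise that all 190 planned events are lasting ones. Section 1.2.2 does not say how often an early eGFR fall amounts to a creatinine doubling. Requiring persistence exchanges dilution for lost events and uneven confirmation, with no assured gain. The conclusion assumes that the counting rule is settled before unblinding.
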